VP-VEC-162-3107
Confidential

Vanda Pharmaceuticals
February 23, 2018

The JET8 study: a double-blind, placebo-controlled study to investigate tasimelteon in healthy subjects with jet lag type insomnia induced by an 8-hour phase advance

Authors:

Document type:

Clinical Study Protocol

Sponsor:

Vanda Pharmaceuticals Inc.
[name]
[name]
[name]

Study Product:

Tasimelteon

Protocol Number:

VP-VEC-162-3107

Study Phase

III

IND Number:

128352

Date: February 23, 2018

Version number Amendment 4

Number of Pages 65

CONFIDENTIAL

This document is confidential and the property of Vanda Pharmaceuticals Inc. No part of it may be transmitted, reproduced, published, or used by other persons without prior written authorization from the study sponsor.

Name of Sponsor/Company: Vanda Pharmaceuticals Inc.	
Name of Investigational Product: Tasimelton/VEC-162	
Name of Active Ingredient: Tasimelton/VEC-162	
Title of Study: The JET8 study: a double-blind, placebo-controlled study to investigate tasimelton in healthy subjects with jet-lag type insomnia induced by an 8-hour phase advance.	
Study center(s): Multicenter (USA)	
Studied period: Estimated date first subject enrolled: October 2017 Estimated last subject enrolled: December 2017	Phase of development: Phase III
Number of subjects (planned): Up to 300 eligible subjects will be randomized and assigned to 20 mg tasimelton or placebo in a 1:1 ratio. Treatment assignments will be made according to a randomization schedule.	
Diagnosis and main criteria for inclusion/exclusion: Healthy males or females 18-75 years of age, inclusive, who meet inclusion criteria.	
Investigational product, dosage and mode of administration: Tasimelton will be administered orally as a dose of 20 mg. Tasimelton dosage form will be size 1, dark blue, opaque, hard gelatin capsules with two white bars on the capsule body and cap, and filled with white to off-white powder.	
Duration of treatment: 1 day/1 night	
Reference therapy, dosage and mode of administration: Placebo capsules will be provided in size and appearance identical to those containing tasimelton and will be administered orally	

CONFIDENTIAL

This material is the property of Vanda Pharmaceuticals Inc. Do not disclose or use except as authorized in writing by the study sponsor.

Objectives:**Primary Objectives:**

1. To assess the effects of tasimelteon 20 mg on nighttime sleep parameters as measured by Polysomnography (PSG) after an 8-hour phase advanced bedtime representative of transmeridian travel across 8 time zones.

Secondary Objectives:

1. To assess the effects of tasimelteon 20 mg on nighttime objective sleep parameters.
2. To assess the effects of tasimelteon 20 mg on nighttime and daytime subjective parameters.
3. To assess the safety and tolerability of single oral doses of tasimelteon 20 mg.

Overall Design:

This is a multicenter, randomized, double-blind, placebo-controlled, parallel pivotal trial to investigate the efficacy and safety of a single 20 mg oral dose of tasimelteon and matching placebo in healthy male and female subjects with jet lag type insomnia from an 8-hour phase advance.

Screening**V1**

IE
KSS
VAS

Evaluation**V2**

KSS KSS
VAS VAS

1 week

In-patient segment
1 day/1 night

Actigraphy and Sleep Diaries

PSG

Tasi or PBO

Pre-Sleep (baseline KSS & VAS)

Post-Sleep (KSS & VAS: 90 minutes after wake then once every 2 hrs)

EOS

CONFIDENTIAL

This material is the property of Vanda Pharmaceuticals Inc. Do not disclose or use except as authorized in writing by the study sponsor.

This study will be divided into 2 phases: the screening phase and the randomization/evaluation phase. The screening phase consists of the screening visit, during which inclusion/exclusion criteria will be assessed and the baseline evaluations will be conducted. The randomization phase consists of a 1-day/1-night double-blind evaluation period in which the subject's bedtime is advanced 8 hours. The screening visit and day/night in sleep clinic will be separated by at least 1 week. Subjects meeting all entry criteria for the study will enter the randomization phase. Eligible subjects will be admitted to a sleep clinic for one day and night of evaluation. Bedtime will be determined by their habitual bedtime (as determined from screening) in the originating time zone. For example, if a subject has a habitual bedtime of 22:00 they will be put to bed at 14:00, or 22:00 in the new "time zone." A PSG will be performed throughout the night beginning prior to bedtime in the "new time zone." Following the 8-hour phase advanced sleep, subjects will complete post-sleep questionnaire, KSS and VAS assessments. During this time subjects will also be provided with breakfast and lunch. After completing all required study procedures, the subjects be discharged from the study clinic. Throughout the study the subject's sleep pattern will be monitored with an actiwatch and through subject reported sleep diaries.

[figure not shown]
[figure not shown]
Statistical Methods:

Nighttime sleep will be assessed by analysis of variance, with treatment group, clinical site, as main effect. A comparison will be made between the subjects treated with tasimelteon 20 mg and placebo. The primary efficacy analysis will be based on the ITT population.

The statistical analyses will be detailed in the Statistical Analysis Plan.

CONFIDENTIAL

This material is the property of Vanda Pharmaceuticals Inc. Do not disclose or use except as authorized in writing by the study sponsor.

7. STATISTICAL PLAN

This section describes the planned statistical analyses in general terms. A complete description of the methodology will be specified in a statistical analysis plan (SAP), which will be finalized prior to unblinding. Any changes in the statistical methods described in this protocol that occur prior to unblinding will be documented in the statistical analysis plan and will not require a protocol amendment.

7.1. General Statistical Design

The study is a multi-center, two-arm, placebo-controlled parallel group pivotal study of the effect of tasimelteon in healthy subjects with jet lag type insomnia. Subjects will be randomized to receive either an active dose of tasimelteon 20 mg or placebo. The primary aim of the study is to ascertain whether tasimelteon is superior to placebo for the reduction of jet lag type insomnia. This study will investigate the effect of treatment on “first-night” jet lag type insomnia by measuring sleep objectively through PSG and the next-day residual effects of treatment. The primary outcome measure is total sleep time (TST) during the first 2/3 of the night (denoted by $TST_{2/3}$) following 8-hour phase advance bedtime, other

CONFIDENTIAL

This material is the property of Vanda Pharmaceuticals Inc. Do not disclose or use except as authorized in writing by the study sponsor.

objective measures (TST in other time intervals, SE, LPS, WASO, Total REM sleep time, total Non-REM sleep time, Latency to REM, and time to accumulate 30 minutes of REM sleep) and subjective next-day effects (KSS and VAS) being secondary outcomes that will provide supportive evidence. The safety and tolerability of tasimelteon will also be explored.

The randomization will be in a 1:1 ratio between the 20mg and placebo groups, and will be stratified by investigative site. The length of follow-up (a screening stage plus day into overnight assessment stage) was chosen in order to assess the “first-night effect” of tasimelteon in healthy volunteers.

7.2. Sample Size and Accrual

The standard deviation is based on data from the tasimelteon Study VP-VEC-162-3101 comparing doses of VEC-162 and placebo in healthy volunteers in a 5 hour phase advance model. To detect a 30 minute difference in TST_{2/3} between tasimelteon-treated subjects versus placebo with a standard deviation (SD) of 75, a sample size of 150 subjects per arm provides approximately 93% power with a two-sided alpha=0.05. This sample size also provides at least 85% power to detect the difference of 28 mins (SD 80) in TST between tasimelteon treated vs. placebo group.

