7.3. Subject Population(s) for Analysis

Three subject populations will be defined for this study:

Intent-To-Treat population: Any subject randomized into the study that received a dose of study drug and had polysomnography data.

All-treated population: Any subject randomized into the study that received a dose of study drug.

Protocol-compliant population: Any subject who was randomized and received the protocol required study drug exposure and required protocol processing.

The primary analyses will be performed on the intent-to-treat population. Secondary analyses of efficacy endpoints will be performed on the protocol-compliant population. Safety summaries will be based on the all-treated population, in which all subjects who receive any study drug are included.

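### Are the stated powers of 93% and at least 85% overstated, because 300 is a ceiling on randomised subjects and the primary analysis set can only be smaller?

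*Combined protocol and SAP*

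**What the plan says.** Protocol Section 7.2 gives two power statements for one sample size.

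- **Primary outcome.** "To detect a 30 minute difference in TST_{2/3} between tasimelteon-treated subjects versus placebo with a standard deviation (SD) of 75", the section says that "a sample size of 150 subjects per arm provides approximately 93% power with a two-sided alpha=0.05".
- **Total sleep time.** "This sample size also provides at least 85% power to detect the difference of 28 mins (SD 80"), the variable being TST with no interval named. I read this as full-night TST, which Section 7.7.2 lists among the secondary outcomes.

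Two other places bear on the number analysed. The Synopsis, under the planned number of subjects, says "Up to 300 eligible subjects will be randomized", and Section 7.1 sets the allocation: "The randomization will be in a 1:1 ratio between the 20mg and placebo groups". Section 7.3 defines the intent-to-treat population, used for the primary analysis, as randomised subjects who "received a dose of study drug and had polysomnography data".

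Section 7.2 does not say whether its 150 are randomised or analysed. The available text gives no expected loss, minimum enrolment or replacement rule.

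**The concern.** Up to 300 subjects split 1:1 means at most 150 per arm randomised. The primary set can equal that number but not exceed it, and it falls by one for every subject who is not dosed or has no usable recording. Both powers are thus computed at the most favourable sample size possible. The wording for TST makes this look worse, because a floor (at least 85%) has been computed at a ceiling and has little slack.

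If losses were material, or enrolment stopped well short of 300, the trial would have less power than Section 7.2 reports, and someone reading that section alone would not see it.

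**Working it through.** **Inputs.** From Section 7.2: two-sided alpha 0.05; difference 30 min with SD 75 (standardised 30/75 = 0.40); difference 28 min with SD 80 (28/80 = 0.35); n = 150 per arm. Allocation is 1:1 (Section 7.1). Loss rates are my assumptions, since the documents give none.

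**Formula.** By normal approximation, power = Φ(δ√(n/2) − 1.96), with δ the standardised difference and n the number analysed per arm. The noncentral t for a two-sample comparison is the check.

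**Reproducing the plan at n = 150.** √75 = 8.660.

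- First two thirds of the night: 0.40 × 8.660 − 1.96 = 1.504, so 93.4% (t: 93.2%).
- TST: 0.35 × 8.660 − 1.96 = 1.071, so 85.8% (t: 85.6%).

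Both stated figures are right.

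**How much loss each statement tolerates.** The required n per arm is 2(1.96 + z)²/δ², where z is the normal quantile of the target power.

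- TST at 85%: 2(1.96 + 1.036)²/0.1225 = 146.6, so 147 (t: 148). That is 294 to 296 analysed in total, a loss of 4 to 6 of 300.
- Primary at 92.5%, which still rounds to 93%: 2(1.96 + 1.440)²/0.16 = 144.5, so 145 (t: 146), or 290 to 292 in total.
- Primary at 90%: 2(1.96 + 1.282)²/0.16 = 131.4, so 132 (t: 133). That is a loss of 17 or 18 per arm, 11 to 12%.
- Primary at 80%: 99 (t: 100), a loss of about one third.

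At exactly 147 per arm, power for TST is 85.1% by the normal approximation and 84.9% by t. Section 7.2 does not say which was used, so whether the claim fails at three lost per arm depends on the method, and the margin is about 0.1 point either way.

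**Power under assumed losses (t to normal).**

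| Loss | Analysed per arm | Primary | TST |
|---|---|---|---|
| 0% | 150 | 93.2–93.4% | 85.6–85.8% |
| 2% | 147 | 92.8–92.9% | 84.9–85.1% |
| 5% | 142.5 | 92.0–92.2% | 83.8–84.0% |
| 10% | 135 | 90.6–90.8% | 81.7–82.0% |
| 15% | 127.5 | 88.9–89.1% | 79.5–79.8% |

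If only 250 were analysed (125 per arm), the powers would be 88.3–88.5% and 78.7–79.0%.

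**Scale.** Power depends on √n/SD, so a 10% loss acts like an SD of 75/√0.90 = 79.1 in place of 75, and a 5% loss like 75/√0.95 = 76.9. Section 7.2 takes its SD from a study with a 5-hour phase advance, whereas this one uses 8 hours. An error of that size in the SD is entirely possible, so the attrition effect lies within the approximation already present in the calculation.

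**What an allowance would buy.** Keeping 150 evaluable under 5% loss needs 150/0.95 = 158 randomised per arm, 16 more in all. It would recover about 1.2 points of primary power (92.0% to 93.2%) and 1.8 points for TST (83.8% to 85.6%).

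**The case for a change.** The strongest case for acting is that a floor should not be calculated at a ceiling. Section 7.2 offers TST as a second support for the sample size, its slack is at most 2% of subjects, and the wording of the Synopsis permits fewer than 300. One sentence stating that 150 means evaluable subjects, with the power at the expected evaluable number, would cost nothing.

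Much of this is accurate. The figures are best case with respect to sample size, and the 85% has almost no reserve. But two stronger claims do not stand. The powers do not need all 300 analysed, as the thresholds above show. Nor are they upper bounds in general: a smaller true SD, or variance explained by site in the analysis of variance planned in Section 7.7.1, would raise them.

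The absence of an allowance is also a statement about the text to hand. It runs from the Synopsis to Section 7, and Section 7 defers full methodology to a separate SAP, so a loss rate or replacement rule may be stated elsewhere. Rewriting the power as a range such as 82 to 86% would put a reviewer's invented 10% loss into the protocol in place of a figure that is correct on its stated condition.

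**Conclusion.** No change is needed. Section 7.2 is a conditional statement (with 150 per arm, power is so much), and on that condition both figures are right. What is missing is the word evaluable and an expected loss, details a statistician supplies without difficulty when reading a power calculation.

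The effect is small. At an assumed 5% loss both powers stay within 2 points of the stated values; at 10% the primary outcome keeps about 91%. The only figure with thin slack belongs to TST, a secondary outcome that Section 7.1 describes as supportive. The design gives little room for attrition: a single dose, with the recording made in the clinic that same night.

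This rests on the plan's own differences and SDs, on enrolment close to 300, and on low loss. If enrolment ended near 200 analysed, power would be 80.4 to 80.7% for the primary outcome and about 69 to 70% for TST. That would be a failure of accrual, not an error in Section 7.2, and it would bias neither the estimate nor the test.

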7.3. Subject Population(s) for Analysis

Three subject populations will be defined for this study:

Intent-To-Treat population: Any subject randomized into the study that received a dose of study drug and had polysomnography data.

All-treated population: Any subject randomized into the study that received a dose of study drug.

Protocol-compliant population: Any subject who was randomized and received the protocol required study drug exposure and required protocol processing.

The primary analyses will be performed on the intent-to-treat population. Secondary analyses of efficacy endpoints will be performed on the protocol-compliant population. Safety summaries will be based on the all-treated population, in which all subjects who receive any study drug are included.

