7.7.2. Secondary outcomes

The secondary outcomes of the study are as follows:

- WASO, as measured by polysomnography. WASO is defined as the time spent awake in the period between onset of persistent sleep and lights on.
- LPS by PSG which is defined as the length of time elapsed between light-out and onset of persistent sleep. Persistent sleep is defined as the point at which 10 minutes of non-wake sleep has begun.
- The full night (as well as parts of the night) SE, defined as the total sleep time (measured by polysomnography) as a percentage of the total time spent in bed between lights off and lights on and full night TST.
- TST in other time intervals of the night, e.g. TST_{3/4} as the total sleep time during the first ¾ of the night (i.e. first 6 hours).
- Total REM sleep time, total Non-REM sleep time, Latency to REM, time to accumulate 30 minutes of REM sleep.
- The subjective post sleep assessments of sleep quality, sleep latency, and total sleep time as collected via post-sleep questionnaire.
- The next day residual effects of tasimelteon:
KSS, VAS and post-sleep questionnaire (PSQ)
- The safety and tolerability of 20 mg tasimelteon.

For the continuous secondary efficacy variables, descriptive statistics will be presented by treatment group, and the scores will be summarized and analyzed in a manner similar to that for the primary endpoint. When baseline is available for endpoint, analysis of covariance will be used by including baseline as a covariance. Categorical variables will also be summarized and evaluated. Details of the analysis will be described in the SAP.

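### Does requiring PSG data for the intent-to-treat set wrongly exclude subjects from the KSS, VAS and post-sleep questionnaire analyses?

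*Combined protocol and SAP*

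**What the plan says.** Section 7.3 defines three sets.

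- **Intent-to-treat:** "Any subject randomized into the study that received a dose of study drug and had polysomnography data". The primary analyses use this set.
- **All-treated:** randomised and dosed, with no PSG condition. Its one stated use is safety: "Safety summaries will be based on the all-treated population, in which all subjects who receive any study drug are included".
- **Protocol-compliant:** randomised, with the required exposure and the required protocol processing, a term that is not explained further. Its use is given as: "Secondary analyses of efficacy endpoints will be performed on the protocol-compliant population".

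Some secondary outcomes do not come from PSG. Section 7.7.2 lists, as next-day residual effects, "KSS, VAS and post-sleep questionnaire (PSQ"), and also takes subjective sleep quality, latency and total sleep time from the questionnaire. Section 7.1 describes "subjective next-day effects (KSS and VAS) being secondary outcomes that will provide supportive evidence". The synopsis gives them an objective, "To assess the effects of tasimelteon 20 mg on nighttime and daytime subjective parameters", and a time: "Following the 8-hour phase advanced sleep, subjects will complete post-sleep questionnaire, KSS and VAS assessments".

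For continuous secondary outcomes, section 7.7.2 follows the approach of the primary endpoint, which under section 7.7.1 is a model with treatment and site. It adds: "When baseline is available for endpoint, analysis of covariance will be used by including baseline as a covariance". It names no analysis set for these outcomes and leaves the detail to the SAP. The introduction to section 7 says that the full methodology will be in a SAP finalised before unblinding, and that changes of method before then need no protocol amendment.

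**The concern.** A set called intent-to-treat that depends on having a post-randomisation measurement is really a modified intent-to-treat set. For a PSG outcome the condition only removes subjects who have no outcome to analyse. For KSS, VAS and the questionnaire it could remove subjects whose outcome was observed, because a different measurement is missing. The planned model for these outcomes has no PSG term, so the exclusion has no analytic purpose.

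The other two sets do not clearly rescue such a subject. All-treated would include the subject but is assigned to safety. Protocol-compliant would probably exclude the subject, since a PSG recording is the central procedure of the study night. At stake would be some precision in the next-day and subjective sleep comparisons and, if absence of PSG were related to treatment, their comparability between arms.

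**Working it through.** **1. Which set applies to the questionnaire outcomes?** The wording in section 7.3 can be read in two ways.

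- *Supportive re-analysis.* The sentence speaks of secondary analyses of efficacy endpoints, not of analyses of secondary endpoints. The ordinary meaning is that intent-to-treat is the main set and protocol-compliant is used to repeat the efficacy analyses. Section 7.7.2, which treats secondary outcomes like the primary, fits this. KSS, VAS and the questionnaire then already have a set: intent-to-treat.
- *Main set for secondary outcomes.* Protocol-compliant would then apply, and whether a subject without PSG is excluded turns on an unexplained term.

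Neither reading clearly keeps the subject. The first gives an ordinary, usable analysis.

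**2. Who would be lost?** The subject must be randomised and dosed, have no PSG data at all, and still complete the assessments after sleep. By the synopsis, PSG starts before bedtime and runs through a single clinic night. Section 7.3 asks only that PSG data exist, not that the recording be complete, so a partial recording keeps the subject in the set. The documents do not suggest that any such subject is expected.

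**3. How much precision could be lost?** The plan gives no figure for absent PSG, so there is none to reproduce. The only input is 150 subjects per arm (section 7.2). Let k per arm be left out. This k is assumed; nothing in the documents fixes or bounds it. For a given k, the loss is greatest if all k completed the questionnaires.

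With equal arms and a common SD, the standard error of the difference is SD × √(2/n), so the interval width changes by the factor √(150/(150 − k)).

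| k per arm | Share of arm | Factor | Widening |
|---|---|---|---|
| 1 | 1/150 = 0.7% | √(150/149) = 1.003 | 0.3% |
| 3 | 3/150 = 2.0% | √(150/147) = 1.010 | 1.0% |
| 8 | 8/150 = 5.3% | √(150/142) = 1.028 | 2.8% |

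**4. Could it bias the comparison?** If a share f of an arm is left out, that arm's mean moves by f × (mean of those kept − mean of those left out). Suppose, as an assumption, that those left out differ by a full SD. The arm mean then moves by 0.007, 0.02 or 0.053 SD for the three values of k. The standard error of the difference with 150 per arm is √(2/150) = 0.115 SD. A shift common to both arms cancels; only a difference between arms would bias the result. Nothing in the documents points to one.

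**5. Does it affect the power statement?** No. The powers in section 7.2 concern total sleep time, which needs PSG in any case. At 150 per arm they reproduce: 93.2% for 30 minutes with SD 75, and 85.6% for 28 minutes with SD 80 (two-sided 0.05, noncentral t).

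**The case for a change.** The strongest case for acting is that the repair is nearly free. Two or three sentences would label the PSG-conditioned set as modified intent-to-treat and place KSS, VAS and the questionnaire in all dosed subjects who have the assessment, as randomised. No subjects, data or imputation would be added. Section 7.3 already fixes definitions and uses, so a SAP that copied it would carry the gap forward, and choosing the set after unblinding would be a data-dependent choice in a pivotal trial. Nor can residual effects simply be treated as safety data: section 7.7.2 lists safety as a separate item, and section 7.8 does not cover these scales.

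Part of this stands. The label is loose, and the protocol names no set for these outcomes. But the label misleads nobody who reads the definition beside it, and renaming it changes no result. Keeping the protocol-compliant set for supportive re-analysis is what section 7.3 already says on its ordinary reading. Naming sets by endpoint is normal SAP content, and the SAP is due before unblinding, which answers the worry about a late choice. Using one set for objective and subjective efficacy outcomes is also a defensible choice: every efficacy table then describes the same subjects, whereas the alternative gives different denominators by endpoint for outcomes that the plan calls supportive.

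**Conclusion.** No change is needed. The text does place a dosed subject without PSG outside intent-to-treat and names no other efficacy set for the questionnaire outcomes, but this is detail that the analysts would settle sensibly when writing the SAP. Followed as written, with intent-to-treat as the main set, the plan would still give sound results for KSS, VAS and the questionnaire.

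The likely effect is close to nil. It reaches 2.8% wider intervals only if 8 of 150 subjects per arm had no recording at all and all of them completed the questionnaires. The conclusion rests on two points: that having PSG data means having any recording, and that complete absence of PSG is rare in a supervised one-night stay. The documents give no rate to confirm the second. The SAP text was not available here, so whether it names the set is unknown. The primary analysis and the sample size are not affected.
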